## **19. Safety Monitoring Analyses**

The Data Safety Monitoring plan (DSMP) contains further detail, but we briefly summarize the general framework here. Safety monitoring analyses will be prepared for the external Independent Monitoring Committee (IMC) align with the IMC meeting schedule (see DSMP for exact schedule).

### **19.1 Adverse Event**

A non-serious AE will be defined as an unfavorable and unintended diagnosis, symptom, syndrome, or disease that occurs or worsens during the acupuncture intervention period and is plausibly related to acupuncture, including bleeding and needling pain. AEs will be collected in multiple ways: (1) during 3-, 6- and 12-month follow up assessments by querying whether the participant believed that anything about their acupuncture treatments caused significant discomfort or pain and, if so, how long that lasted; (2) via electronic acupuncturist treatment reports; and (3) from participants who may phone the study team at any time to report AEs. Because acupuncture has relatively short-term physiological effects, we will not report AEs that first manifest more than 30-days after a participant's final acupuncture treatment.

We will classify each non-Serious AE using the following definitions: Mild (transient or minimal symptoms; no changes in activity level; no therapy or only symptomatic therapy); Moderate (symptomatic with moderate changes in activity level; no decrease in social activities; specific therapy required); Severe (incapacitating; bed rest; substantial decrease in social activities; loss of work). These definitions are consistent with the International Council for Harmonisation (ICH) standards in characterizing AEs. In the unlikely event that an adverse effect occurs that requires medical care, treatment will be provided as covered by participants' existing health care coverage. We will also assess the likely relatedness of the adverse event and acupuncture given the nature of the event, the timing related to treatment and any important contextual factors.

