6.2.3 Blinding

This is an unmasked trial for participants, although the acupuncture participants will not know whether they are in the SA group or EA group until 10 weeks into the standard treatment period. Interviewers will be masked to treatment group for all standard study assessments. For qualitative data collection, interviewers are expected to be unmasked to participants treatment condition. Acupuncturists will not know whether their patients are in the SA or EA group until 10 weeks into the standard treatment period.

No members of the Core Executive Team (Multiple PI's, site PI's and the Statistical Methods Committee, which includes the study biostatisticians) will have access to the outcomes data during the trial. Conceivably, a site PI or one of the Multiple PI's may become aware of an individual's treatment group if they have an Adverse Event that requires the investigator intervene. One biostatistician, [name], may be supervising some data collection exercises with the programmers as needed, but datasets will not contain a treatment assignment variable prior to the locking of the database. All other members of the CEC will become unblinded after the data base is locked.

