AEs reported by patients to their acupuncturists or study staff will be recorded and reported to appropriate regulatory bodies (single IRB and Independent Monitoring Committee (IMC)). Acupuncturists will record AEs on their treatment forms but alert the research team immediately if they are concerned about any AE or learn a participant is injured, needs hospitalization, trip to the emergency department or medical attention. In addition, patients will have the phone numbers of study staff to report any side effects they are concerned about in real time. We will collect data on “health problems that have interfered with your functioning for a few days or more that you think may have been caused by your study acupuncture treatment” using a mailed questionnaire sent to all acupuncture-randomized participants at 3 months after randomization and enhanced acupuncture participants again at 6 months after randomization. Any positive responses will be reviewed by study medical personnel and followed up by study personnel to obtain additional information on the patient’s condition, whether it has resolved or not, how long that took and whether the patient needed to modify their activities. The previous AE form we used for an acupuncture study (which we filled out based on data from the follow-up interview) included: anxiety, bruising, dizziness, fainting, fatigue, headache, nausea/vomiting, pain from needle insertion or stimulation, and other pain (including increased back pain). We graded non-serious AEs as mild, moderate and severe. We also included information on relatedness to treatment (definitely, probably, possibly, definitely not). Note, increased back pain is an expected variation in the natural history of cLBP and, as such, would not without concomitant disability be considered an AE for this study.

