data every month to identify deaths and hospitalizations among enrolled participants. In the case of a death, a chart review will be conducted by a physician at the clinical site to assess whether the death was related to the study intervention (definitely, probably, possibly, or unrelated to the study intervention). For hospitalizations, a study clinician at each HCS will review the list of diagnoses for possible relatedness to the acupuncture intervention. For any diagnosis at least possibly related to acupuncture, a more in-depth examination of the medical chart will be conducted. Because the number of hospitalizations in our older adult study population may be high and acupuncture poses only minimal risk, we do not plan to chart-review hospitalizations as a matter of course. However, if our analytic reports suggest a possible increased risk of hospitalizations associated with acupuncture, we will work with our monitoring groups to develop a plan to do chart reviews on all or a subset of patients charts who were hospitalized. A non-serious AE will be defined as an unfavorable and unintended diagnosis, symptom, syndrome, or disease that occurs or worsens during the acupuncture intervention period and is plausibly related to acupuncture. We believe this definition is appropriate, given that older adults have many diagnoses, symptoms, and syndromes, most of which would be expected to be of longer duration and unrelated to acupuncture, for which AEs have typically been shown to be relatively brief in duration. Non-serious AEs will be collected in multiple ways: (1) at 3 and 6 months using a mailed questionnaire sent to all acupuncture-randomized participants at 3 months after randomization and enhanced acupuncture participants again at 6 months after randomization asking about “health problems that have interfered with your functioning for a few days or more that you think may have been caused by your study acupuncture treatment” ; (2) from participants who may phone the study team at any time to report AEs; and (3) via electronic acupuncturist treatment reports for events that occur or were reported in the acupuncturist’s office. Because acupuncture has relatively short-term physiological effects, we will not report AEs that first manifest more than 30 days after a participant’s final acupuncture treatment.

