10. DATA COLLECTION AND QUALITY ASSURANCE

10.1 Data Collection Forms

Staff at KPWHRI will develop the oral eligibility screening language and the baseline, monthly, 3, 6 and 12-month follow-up questionnaires. After consent, all sites will transfer data on participants to the centralized data capture system, Discovery, at KPWHRI. Data collection at baseline will be conducted by site staff using Discovery. KPWHRI Survey Research Program will do all follow-up assessments. These will be done by computer assisted telephone interviewing (CATI at 3-, 6-,12-month follow-ups), web (3-, 6-,12-month follow-up and monthly) or both, depending on the needs to each participant. These data will be considered primary source data. All interviewers will be masked to treatment group.

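### SAP 19.1 asks about acupuncture harms inside the follow-up assessments that collect the RMDQ, which can unmask telephone interviewers; the protocol uses a separate mailed form, and the documents disagree on adverse-event timing and wording

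*SAP*

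**What the plan says.** **SAP.** Section 19.1 lists three sources of non-serious adverse events. The first is a question to participants, put "during 3-, 6- and 12-month follow up assessments by querying whether the participant believed that anything about their acupuncture treatments" caused marked discomfort or pain, and for how long. The other two are acupuncturists' treatment reports and calls from participants.

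**Protocol.** Section 7.2 describes a "mailed questionnaire sent to all acupuncture-randomized participants at 3 months after randomization and enhanced acupuncture participants again at 6 months". Section 7.3 repeats this route and these recipients. The question concerns "health problems that have interfered with your functioning for a few days or more that you think may have been caused" by the study acupuncture.

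**Outcome collection.** RMDQ and PEG are part of the 3-, 6- and 12-month follow-up. Protocol 10.1 states that "KPWHRI Survey Research Program will do all follow-up assessments", by computer-assisted telephone interview, by web, or both. Protocol 6.2.4 lets the participant choose the mode.

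**Masking.** Protocol 6.2.3 states: "Interviewers will be masked to treatment group for all standard study assessments". Section 10.1 repeats the commitment, and section 4.3.4 assigns follow-up to a different interviewer from the one who randomizes, for this reason. The blinding text in SAP Section 7 mentions only the qualitative interviewers, who are expected to be unmasked.

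**The concern.** The primary outcome is self-reported by participants who know whether they were assigned to acupuncture. Masking the person who asks the questions is one of the few protections left when the RMDQ is collected. A question about the participant's acupuncture treatments, asked in the same telephone contact, works against that protection. The affected contrast is acupuncture versus usual medical care, which is the main comparison of the trial.

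The second stake is the safety table. SAP 19.5 summarizes safety outcomes by intervention. Who is asked, when, and at what threshold determines what is counted, and the two documents give different answers on all three.

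**Working it through.** No sample size, power or event figure is involved. The check is a comparison of texts and one calculation of the reporting window.

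**1. The passages side by side**

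| Source | Route | Recipients | Timepoints | Threshold |
|---|---|---|---|---|
| SAP 19.1 | within the follow-up assessment | no arm restriction stated | 3, 6, 12 months | marked discomfort or pain |
| Protocol 7.2, 7.3 | separate mailed form | both acupuncture arms at 3 months, EA only at 6 | 3, 6 months | several days of interference with functioning |
| Protocol 6.1 schedule | acupuncture visits and follow-up | not stated | tick under the 3, 6, 12 months column | not stated |
| Protocol 6.2.2 measures table | participant report, health record, treatment records | not stated | footnote: 3 and 6 months only | not stated |
| SAP 19.3 | questionnaires | not stated | 3 and 6 months | not stated |

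The SAP and the protocol differ on route, recipients, timepoints and threshold. Each document also disagrees with itself on 12 months: SAP 19.1 against 19.3, and the protocol's 6.1 schedule against its 6.2.2 measures table.

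**2. How the SAP route could unmask a telephone interviewer**

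- If the item is asked of everyone, the answer tends to show whether the participant had acupuncture.
- If the item is programmed to appear only for the acupuncture arms, its appearance shows the arm.
- If it comes before the RMDQ, the RMDQ in that call is exposed. If it comes after, that RMDQ is protected, but an interviewer who learned the arm at 3 months could collect the 6-month RMDQ. Neither document rules this out.
- The item mainly separates acupuncture from usual medical care, not standard acupuncture (SA) from EA.
- Web completers have no interviewer. The telephone/web split is not given.

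**3. Which timepoints cover the reportable window**

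Both documents limit reporting by onset. In the words of Protocol 7.3, "we will not report AEs that first manifest more than 30 days after" the final treatment. Inputs: SA lasts about 90 days and EA adds about 3 months, so it ends at about day 180 (protocol précis).

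- SA: 90 + 30 = day 120 is the last reportable onset.
- EA: 180 + 30 = day 210 is the last reportable onset.
- The first visit is requested within 10 days of randomization, so these could move to about day 120 + 10 = 130 and day 210 + 10 = 220.

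Under the protocol's mailing schedule, the last SA form goes out at about day 90 and the last EA form at about day 180. That leaves 120 − 90 = 30 days in SA and 210 − 180 = 30 days in EA in which a reportable event could start after the last solicited query. Under the SAP schedule, the 6-month query falls 180 − 120 = 60 days after the SA window closes, and the 12-month query falls 365 − 210 = 155 days after the EA window closes. Both windows are covered, but by longer recall.

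**4. Size of any bias**

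It would depend on the share followed by telephone, the share of those interviewers who learn the arm before asking the RMDQ, and the shift in answers that this causes. The documents give none of the three, so no figure is offered.

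**The case against.** The strongest reply is that SAP 19.1 may be loose or outdated text. SAP Section 19 presents itself as a short summary and defers to a data safety monitoring plan that is not among the documents. The protocol describes operations in more detail, with masked interviewers and a mailed form. SAP 19.3 names only 3- and 6-month questionnaires, as the protocol does. The protocol's revision history also records that its measures table was updated to match approved procedures for adverse-event questions. Nothing shows that masked interviewers ask this question, or ask it before the RMDQ. This stands: the documents show a route that would unmask if followed, not that unmasking happens. The texts still conflict, and the SAP states no safeguard.

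A reader might also infer three stronger things that the documents do not support.

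- **That the 12-month query could yield nothing reportable, so dropping it costs nothing for safety.** The 30-day rule limits when an event starts, not when it is asked about. A later query can still elicit events that started within the window, and the protocol's schedule leaves a gap of about 30 days in each arm without a solicited query. Treatment reports stop with the last visit, so only spontaneous calls would remain.
- **That interviewer masking is the trial's only masking.** SAP Section 7 assigns the primary analyses to a fully blinded biostatistician. Participants and acupuncturists do not know SA from EA until about week 10.
- **That the protocol is the clean version.** Its own tables disagree on 12 months. Its measures table also has a 12-month participant item on acupuncture use, which could unmask an interviewer, although only after the primary time point.

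**Conclusion.** The concern holds as a conflict between the documents with a specific risk to masking. Followed as written, SAP 19.1 can reveal acupuncture versus usual medical care to telephone interviewers who are meant to be masked when they collect the RMDQ, either in that call or in a later one. This rests on three assumptions: that some follow-up is by telephone, that the item is asked by the person who collects the RMDQ, and that it comes before the RMDQ or that the same interviewer handles a later assessment. Any resulting bias is of unknown size, and no effect on the primary result is shown.

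The disagreement on route, recipients, timepoints and wording stands regardless of masking, because it determines which adverse events reach the by-arm summary. It should be corrected, and the correction is cheap.

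**What to change.** 1. Change the first source in SAP 19.1 to the protocol's separate adverse-event form, outside the masked outcome interview.
2. State in both documents that no adverse-event or acupuncture-use item precedes RMDQ and PEG in a masked interview. State also that adverse-event answers are withheld from outcome interviewers, including when positive answers are followed up. Add the masking of standard assessments to SAP Section 7.
3. Reconcile Protocol 6.1, the 6.2.2 measures table, 7.2 and 7.3 with SAP 19.1 and 19.3 on route, recipients, timepoints and question wording.
4. When choosing the timepoints, check that they cover events starting up to 30 days after the last treatment in each arm. A later query can be kept on the separate form without touching the masked interview.
5. If telephone interviewers have already asked the SAP question, record where it sat relative to the RMDQ and report it as a limitation of masking.

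The cost is mainly wording, since the protocol already describes the mailed form. The real loss is interview-based recall of adverse events, so return of the separate form needs tracking. If the timepoints are extended to close the 30-day gaps, there is also an added mailing.

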### **19.2 Serious Adverse Event**

For the proposed study, we are operationally defining a serious adverse event (SAE) as a death or hospitalization, prolongation of a hospitalization or other serious or life-threatening event during a patient's active participation in the trial and study acupuncture treatments. We will review/query active study participants' EHR data every month to identify deaths and hospitalizations among enrolled participants. In the case of a death, a chart review will be conducted by an independent physician at the clinical site to assess whether the death was related to the study intervention (definitely, probably, possibly, or unrelated to the study intervention). For hospitalization, a study clinician at each HCS will review the list of diagnoses for possible relatedness to the acupuncture intervention. For any diagnosis at least possibly related to acupuncture, a more in-depth examination of the medical chart will be conducted.

### **19.3 AE/SAE Reporting Procedure**

A report of AEs will be reviewed by the PIs and Co-Investigators every month and by the IMC every six months. Reports of AE's will be reviewed from the 3 and 6-month questionnaires at regular study meetings. They will be signed off by the Site PI and a study physician. If acupuncturists or patients report an AE, study staff will complete an AE form and follow-up with the patient as appropriate. Serious adverse events that are at least possibly related to acupuncture will be dealt with as soon as the study staff are aware of them. Non-serious AE's will be reported to the IRB yearly and to the IMC at the next meeting. Incidents or events that meet the OHRP criteria for unanticipated problems will be reported to the IRB and the BIA IMC. We will report Unanticipated Problems to our NCCIH Program Officer and OCRA and the BIA IMC by submission of an Unanticipated Problem Report via secure email to NCCIH and fax or email to the IMC chair.

## 19.4 Safety Outcomes

See DSMP for specifics.

## 19.5 Descriptive Analysis

The safety outcomes will be summarized by type and by intervention in terms of frequency of the event in each individual, number of participants having the event, timing relative to randomization, and relatedness to the study treatment (definitely, probably, possibly, definitely not). As acupuncture is a relatively safe treatment, we anticipate incidence of possibly treatment related hospitalizations and deaths to be relatively rare so do not propose any formal statistical tests of the SAE data.

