2. BACKGROUND AND RATIONALE

2.1 Background on Condition, Disease, or Other Primary Study Focus

Back pain is the leading cause of disability worldwide, with both prevalence and burden increasing with age.¹ In the United States, about \$86 billion is spent annually on direct costs of medical care for back/neck pain,² with particularly marked escalating costs for back pain in older Americans (those at least 65 years of age). While the Medicare population increased only 42% between 1991 and 2002, expenditures for back pain increased 387%.³ Despite these large investments in care for back pain,⁴ the health and functional status of Americans with back pain has deteriorated.² Roughly a quarter of older adults report low back pain⁵ with prognosis worsening with age.⁶ Persistent pain, typically lasting three months or longer, is the most consequential type of back pain.

A critical gap exists in the evidence on the safety and effectiveness of treatments for older adults with cLBP. This gap is of particular concern because about 12% of adults age 65 and over suffer from impairing cLBP,⁷ the prevalence is increasing⁸ and older adults commonly have more disabling back pain than those under age 65.⁶ Many treatments considered appropriate for adults under age 65 may not be appropriate for older adults given their greater prevalence of comorbidities with attendant polypharmacy.⁹ In addition, burgeoning imaging rates reveal incidental pathology in many cases, placing older adults at risk for inappropriate invasive treatments.^{8,10} Because of normal physiological changes with aging (e.g., reduced tolerance of medications and increased prevalence of osteoporosis), older adults are at substantially increased risk of adverse effects of commonly used LBP treatments^{7,11-13} including medications (e.g., non-steroidal anti-inflammatory drugs [NSAIDs], muscle relaxants, and opioids) and complementary and integrative (CIM) treatments such as high velocity spinal manipulation techniques. While numerous randomized clinical trials (RCTs) have evaluated treatments for

chronic pain, their applicability to older adults is unclear because most of these RCTs included few, if any, older adults.

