## 5.3 Safety Analysis Sample

The safety analysis will include all randomized participants in the sample in the 12-months period of follow-up.

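### Safety is to be tabulated by arm over all randomised participants, but the only active ascertainment common to all arms is the EHR query for deaths and hospitalizations

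*SAP*

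**What the plan says.** **Sample and display.** SAP 5.3: "The safety analysis will include all randomized participants in the sample in the 12-months period of follow-up". SAP 19.5: "The safety outcomes will be summarized by type and by intervention in terms of frequency of the event in each individual". Nothing in either section confines the AE tables to the acupuncture arms, sets a rule on data source, or warns that ascertainment differs. SAP 19.5 adds that the authors "do not propose any formal statistical tests of the SAE data". SAP 19.4 leaves the list of safety outcomes to the DSMP.

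**Collection of non-serious AEs.** Protocol 7.2 and 7.3 describe a mailed form, "sent to all acupuncture-randomized participants at 3 months after randomization and enhanced acupuncture participants again at 6 months after randomization". It asks about health problems "that you think may have been caused by your study acupuncture treatment". The other routes are the acupuncturists' treatment reports and calls from participants to the study team. Protocol 7.3 and SAP 19.1 both require a non-serious AE to arise or worsen in the acupuncture period and to be plausibly attributable to acupuncture. Both also close the reporting window 30 days after the last treatment.

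**Collection of SAEs.** Protocol 7.3 and SAP 19.2 search the EHR monthly for deaths and hospitalizations among enrolled participants. Protocol 7.2 also tells acupuncturists to alert the team at once if they "learn a participant is injured, needs hospitalization, trip to the emergency department or medical attention". The SAE definition includes a residual class of other serious or life-threatening events, for which no search covering all arms is described.

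**Chart-review trigger.** Protocol 7.3 plans wider chart review if reports suggest more hospitalizations with acupuncture.

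**The concern.** A table by arm invites comparison across its columns, and that is fair only if events were looked for in the same way in each. Here the UMC column would show no non-serious AEs because none can be defined or asked about there, yet a printed 0 looks like an observed rate. SAEs outside the EHR query have extra routes to detection in SA and EA, so equal true risk could appear as an excess with acupuncture. With no formal tests, readers and the monitoring committee will judge the raw counts by eye. The hospitalization count also matters for trial conduct, because it feeds the chart-review trigger. The SAP does not say whether admissions known only through acupuncturists are added to the EHR count.

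**Working it through.** **1. Denominators.** Protocol 9.2 needs 210 evaluable per arm with 20% loss: 210/(1 − 0.20) = 262.5, rounded up to 263, and 3 × 263 = 789. The plan's figure reproduces. A table under SAP 5.3 would therefore have about 263 in each column.

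**2. Routes by arm, as the protocol describes them.**

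| Route | SA | EA | UMC |
|---|---|---|---|
| Study acupuncture visits with AE report | up to 15 | up to 15 + 6 = 21 | none |
| Acupuncturist alert on injury, admission, emergency or medical care | yes | yes | none |
| Mailed harm form, per participant | 1 (month 3) | 2 (months 3 and 6) | 0 |
| Mailed harm forms, per arm | 263 | 2 × 263 = 526 | 0 |
| Participant phones in (passive) | yes | yes | yes |
| Monthly EHR query: deaths, hospitalizations | yes | yes | yes |

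Only the last row is both active and common to all arms.

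**3. Non-serious AEs.** As an illustration, take the 2.3% moderate-AE rate that the protocol quotes from an earlier acupuncture trial. Expected events in the two acupuncture arms are 0.023 × 526 = 12.1. At 1% and 10%, the range the protocol gives for bleeding and hematoma, they are 5.3 and 52.6. UMC would show 0 of 263, crossovers aside. Read as data, 0/263 has an exact two-sided 95% upper limit of 1 − 0.025^(1/263) = 1.4%. That precision does not exist, because the question was not put to UMC. Pooling over all randomised participants would also dilute 2.3% to 12.1/789 = 1.5%.

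**4. SAEs outside the EHR query.** Assume a true risk of 2% in every arm and full capture in SA and EA. Each acupuncture arm then expects 0.02 × 263 = 5.3 events. UMC shows 0, 1.3, 2.6 or 5.3 if 0%, 25%, 50% or 100% of its events become known. Neither the risk nor the capture share is in the documents. The sketch shows only that the visible contrast would be set by the capture share, which is unknown.

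**5. EHR completeness.** Protocol 9.6 says that the IFH record holds incomplete hospitalization data. IFH's recruitment target is 123 of 789, or 15.6%. This affects all arms at that site, but an acupuncturist report can fill the gap only in SA and EA.

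**6. EA against SA.** Only EA receives the 6-month form, and only EA has visits in months 4 to 6. Some EA excess is therefore built into totals over the whole period. Over months 0–3 the planned routes are the same in both arms.

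**7. Texts that disagree.**
- SAP 19.1 asks about AEs at 3, 6 and 12 months and names no arm. Protocol 7.2 and 7.3 restrict the form to SA and EA at month 3 and EA at month 6.
- Within the protocol, the schedule in 6.1 marks AEs at 3, 6 and 12 months, while the footnote to the measures table in 6.2.2 says 3 and 6 months only.
- SAP 19.2 ties the SAE window to study acupuncture treatments as well as trial participation. The protocol's SAE definition does not, and the added condition has no clear meaning for UMC.

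**The case against.** The definition of a non-serious AE is deliberate. Protocol 7.3 explains that older adults have many symptoms and diagnoses unrelated to acupuncture, so a table of acupuncture-related AEs rightly has almost nothing in UMC. No aim compares the harms of acupuncture with those of usual care. The display is descriptive, and the DSMP may already limit the tables by arm. SAP 19.1 names no arm, so the SAP alone does not exclude UMC from the AE query. A false hospitalization signal would lead only to a plan for more chart review.

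Most of this stands, and it rules out three stronger readings that a reader might infer:

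- *That UMC is zero by construction for all safety outcomes.* Deaths and hospitalizations come from the same EHR query in every arm, and UMC participants may phone in other serious events.
- *That the plan conceals usual-care harms it set out to measure.* Protocol 2.1 does say that "older adults are at substantially increased risk of adverse effects of commonly used LBP treatments", but this is background. Adverse reactions to usual care are not AEs under the plan's definition, and wanting them counted is a different design choice.
- *That the inflation of hospitalizations can be calculated.* This would need the share of admissions missed by the EHR and the share of those that acupuncturists hear of. The documents give neither, and they do not say that alerts are added to the EHR count.

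The objection does not remove the core point. The SAP query still concerns only acupuncture treatments, so it gives a UMC participant without acupuncture nothing to report. The SAP as written still sets unequally ascertained counts side by side.

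**Conclusion.** The point holds in a limited form. Across all three arms, only EHR-query deaths and hospitalizations are ascertained alike, subject to incomplete capture at IFH. For non-serious AEs, a UMC 0 is not an observation; it follows from the definition as much as from the collection. For other SAEs, and for admissions missing from the EHR, UMC is under-ascertained by an amount the documents do not allow one to estimate. The counts in the working rest on quoted or assumed rates and are illustrations only. The conclusion assumes that AE collection follows Protocol 7.2 and 7.3 and that the DSMP adds no restriction. No sample size, power figure or effectiveness analysis is affected. The change is worth making because it is cheap and removes a detection bias from the safety tables and from the chart-review trigger.

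**What to change.** In SAP 5.3 and 19.5:

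1. Limit the three-arm safety table to deaths and hospitalizations found by the monthly EHR query over the same 12 months in every arm. Note the incomplete hospitalization capture at IFH. Base the Protocol 7.3 hospitalization trigger on these counts. List SAEs known only from acupuncturists, forms or calls separately, with a source flag.
2. Tabulate acupuncture-attributed non-serious AEs for SA and EA only, and mark UMC as not ascertained or not applicable. Report events in UMC participants who obtained acupuncture separately. Show SA and EA over months 0–3 as well as overall.
3. Reconcile Protocol 7.2 and 7.3, the schedule and measures tables in Protocol 6.1 and 6.2.2, and SAP 19.1 on who is asked about AEs and when. Reconcile the SAE window in SAP 19.2 with the definition in Protocol 7.3. Check that the DSMP agrees.

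The cost is SAP wording and a source field on SAE records. The downside is that the three-arm table covers fewer event types. A neutral health-problem item in the 3- and 6-month surveys of all arms is optional and not needed for this fix. If added partway, it would make ascertainment depend on calendar time, and positive answers would need medical review.
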